4.0 Study Population (Inclusion/Exclusion Criteria)

Inclusion criteria:

- 1. Between 18 and 40 years of age
- 2. Within 10 years of illness onset as defined by entry into treatment for psychotic symptoms
- 3. Able to give informed consent
- 4. Willing and able to adhere to the study schedule
- 5. Structured Clinical Interview for DSM-5 (SCID-5-RV) diagnosis of schizophrenia
- 6. Clinical stability defined by:
 - a. Subjects must not have experienced an exacerbation of their illness within 4 weeks prior to randomization, leading to an intensification of psychiatric care in the opinion of the investigator. Examples of intensification of care include, but are not limited to: inpatient hospitalization, day/partial hospitalization, outpatient crisis management, or psychiatric treatment in an emergency room AND

b. Antipsychotic treatment stability for at least 4 weeks prior to randomization (no change in antipsychotic dosing or addition of new antipsychotic medication)

Exclusion criteria:

- 1. Lifetime history of a seizure, excluding febrile seizures and those induced by substance withdrawal
- 2. First degree relative with idiopathic epilepsy or other seizure disorder
- 3. History of significant neurological illness
- 4. History of head trauma as defined by a loss of consciousness or a post-concussive syndrome
- 5. Pregnant or breast feeding
- 6. Known IQ < 70 based on subject report
- 7. Current acute, serious, or unstable medical conditions
- 8. Metallic objects planted in or near the head, including implanted pacemaker, medication pump, vagal stimulator, deep brain stimulator, TENS unit, ventriculoperitoneal shunt, or cochlear implants
- 9. Contraindications to MRI or otherwise unable to tolerate MRI procedures
- 10. History of electroconvulsive therapy
- 11. Subjects taking clozapine
- 12. Subjects who have participated in a clinical trial with any pharmacological treatment intervention for which they received study-related medication in the 4 weeks prior to randomization
- 13. Subjects considered a high risk for suicidal acts active suicidal ideation as determined by clinical interview OR any suicide attempt in 90 days prior to screening
- 14. Current DSM-5 diagnosis of alcohol or drug use disorder (excluding nicotine or caffeine)
- 15. Subjects who require concomitant treatment with prohibited medication, as specified in Attachment 2

5.0 Subject Recruitment

Subjects will be recruited through referring community mental health centers, treatment providers, the IUPDP registry, and self-referrals through advertisement and word-of-mouth.

6.0 Clinical Assessments and Procedures

The following assessments will be administered according to the Study Procedures Table (Attachment 1). All assessments will be completed by study personnel trained to administer the instruments and will be based on interviews with the subject or questionnaires completed by the subject.

Columbia Suicide Severity Rating Scale (C-SSRS)

The C-SSRS captures the occurrence, severity, and frequency of suicide-related thoughts and behaviors during the assessment period. The definition of behavioral suicidal events used in this scale is based on those used in the Columbia Suicide History Form⁴¹. During the baseline assessment, questions are in relation to lifetime experiences and all subsequent questioning is in relation to the last assessment.

The Positive and Negative Syndrome Scale (PANSS)

The PANSS is the primary assessment instrument for psychopathology. The PANSS contains 30 items that assess symptoms of psychotic disorders including positive, negative and general psychopathology. The PANSS was chosen because of its widespread use in clinical studies of psychosis, and its demonstrated reliability in assessing psychopathology across diverse patient populations⁴².

Diagnostic Interview

The Structured Clinical Interview for DSM-5 (SCID-5-RV) will be used to confirm the diagnosis of a psychotic disorder and/or rule out other diagnoses. The SCID-5-RV is a semi-structured interview designed to evaluate DSM-5 Axis I diagnoses³⁷.

Clinical Global Impressions Severity Scale (CGI-S)

The CGI-S is used for repeated evaluations of global psychopathology⁴³. The CGI-S scale is widely used in schizophrenia research and is a single 7-point Likert scale rating severity of psychopathology on a scale of 1 (normal, not ill) to 7 (very severely ill).

Clinical Global Impressions Severity Improvement Scale (CGI-I)

The CGI-I is used to assess the clinical change as compared to symptoms at baseline using a 7-point Likert scale, ranging from very much improved (1) to very much worse $(7)^{43}$.

Abnormal Involuntary Movement Scale (AIMS)

The AIMS is a 12-item scale designed to record the occurrence of dyskinetic movements⁴⁴. Items 1 to 10 are rated on a 5-point scale, with 0 being no dyskinetic movements and 4 being severe dyskinetic movements. Items 11 and 12 are yes/no questions regarding the dental condition of a subject.

Magnetic Resonance Imaging (MRI) Procedures

Subjects will practice tasks on a personal computer during Visit 1 and prior to the scan at subsequent visits. Subjects will complete all pre-MRI procedures (e.g., completion of MRI screening form) before stimulation sessions to minimize the time in-between the stimulation session and MRI. We intend to conduct post-stimulation scans within fifteen minutes of completing a stimulation session. Siebner et al. (2009) noted in a consensus paper on combining transcranial stimulation with neuroimaging that protocols applying prolonged trains of rTMS can induce changes in neuronal excitability that may last for more than one hour post-TMS⁴⁵. We believe that an interval of 15 minutes between rTMS session and fMRI will capture changes in excitability.

MRI will be performed at the IU Center for Neuroimaging using an integrated 45-minute exam, including structural and fMRI. Scans will be completed on a research-dedicated Siemens MAGNETOM Prisma 3T scanner. Subjects will undergo a high-resolution 3D magnetization prepared rapid gradient echo (MPRAGE) scan for individual anatomical reference. An MRI-compatible response box will be utilized for tasks, recording reaction time and accuracy. fMRI will employ a computerized version of the Stroop Color-Word task. A task-free resting state fMRI scan will also be acquired to measure functional connectivity between CCN structures.

Stroop Color-Word Task

Subjects will perform an in-scanner computerized version of the Stroop Color-Word task. This and similar paradigms have been shown by our group and others to elicit reliable ACC activation during task performance⁴⁶. In this task, stimuli consist of three words: "Red", "Green", or "Yellow", displayed in the

Stroop Color-Word Task

corresponding color. Trials are either "congruent" (word matches ink color), "incongruent," where the word and the color of the word differ in incongruent colors, or "nonwords," which are "XXX", "XXXX", or "XXXXX". The Stroop Color-Word task requires participants to press one of three buttons to identify the ink color of a presented word (red, green, or yellow; randomly assigned). Subjects are instructed to indicate the color but ignore the word and to respond as quickly and accurately as possible via button press. There are multiple iterations of this task available, mitigating potential practice effects. Participants will practice examples of the CC task on a personal computer during Session 1 and prior to the scan at subsequent visits.

Emotional Stroop Color-Word Task

Subjects will also perform an Emotional Stroop Color-Word task during the scan. This task is identical to the standard Stroop Color-Word, except emotional words (e.g., poor, sick, hurt) and neutral words (e.g., note, run, spin) are used instead of congruent and incongruent words. Subjects are again instructed to indicate the ink color of the word via button-press. This task will be practiced prior to each scan as well.

Positioning and motion

Subjects are instructed to remain still during scanning and deformable foam cushioning is used to stabilize the head. Real time image reconstruction and processing are used for quality assurance at the time of scanning. For fMRI, minor subvoxel-level translation or rotation is adjusted during post-processing. Noise: Noise-attenuating headphones and ear stopples provide excellent noise reduction and permit adequate auditory perception.

Functional Imaging Stimulation and Physiological Monitoring Procedures

A comprehensive physiological monitoring system will be used with synchronized digital recording including pulse oximeter, respiratory belt, HR and BP measures, which will be available for analysis in relation to BOLD fMRI time series.

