2.0 Specific Aims and Hypothesis

The **first primary aim** is to define the impact of HF (20 Hz) rTMS targeting the LDLPFC and LSPC on ACC activation in individuals with schizophrenia during in-scanner CC task performance. We predict that HF rTMS targeting the LDLPFC and LSPC will result in increased functional activation in the ACC during performance of an in-scanner CC task. The **second primary aim** of this study is to define the impact of HF rTMS targeting the LDLPFC and LSPC on CCN functional connectivity (FC). We hypothesize that HF rTMS of the LDLPFC and LSPC will result in increased FC between the LDLPFC, LSPC, and ACC during performance of an in-scanner CC task. An **exploratory aim** of this study is to determine the effects of HF rTMS targeting the LDLPFC and LSPC will examine if HF rTMS targeting the LDLPFC and LSPC is associated with improved performance during on in-scanner CC task.

Primary Aim 2 Prediction

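### Alternate Stroop versions cannot prevent task learning, so practice is confounded with rTMS in the baseline-to-post performance comparison

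*Combined protocol and SAP*

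**What the plan says.** Section 6.0 (Stroop Color-Word Task) offers one stated protection against learning: "There are multiple iterations of this task available, mitigating potential practice effects". It does not say how the versions differ or how they are assigned to the three scans.

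The same section limits the words to Red, Green and Yellow and the nonwords to strings of three, four or five X's. Subjects "press one of three buttons to identify the ink color of a presented word (red, green, or yellow; randomly assigned"). Trials are congruent, incongruent or nonword.

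On rehearsal, Section 6.0 states: "Participants will practice examples of the CC task on a personal computer during Session 1 and prior to the scan at subsequent visits". No performance level has to be reached. A second task in the same scan also uses the ink-color response and is also practiced before each scan: "This task is identical to the standard Stroop Color-Word, except emotional words" and neutral words take the place of the color words.

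Section 3.0 and Attachment 1 place the baseline scan at Visit 1, before randomization. Visits 2 and 3 each give one active 20 Hz session followed by a scan. Only the order of the two sites is randomized and counterbalanced.

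The exploratory aim in Section 2.0 asks whether stimulation "is associated with improved performance during on in-scanner CC task". Section 13.0 tests treatment comparisons one-sided at 0.05 by repeated-measures ANOVA. It names no practice or period adjustment and does not define the performance score.

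**The concern.** Alternate forms help when subjects could memorize items. In a Stroop task, what improves with repetition is responding to ink while ignoring the word, and any version built from the same few words and inks rehearses that skill. The stated safeguard does not address this kind of learning.

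The design does not address it either. Scan 1 is always unstimulated, and scans 2 and 3 always follow active stimulation. Any change from baseline therefore mixes rTMS with repetition. Better performance is both what practice produces and what the one-sided exploratory hypothesis predicts. Section 1.0 says the study is meant to inform later trials, so a learning gain reported as a cognitive benefit of rTMS would mislead them.

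**Working it through.** **Step 1: how many stimuli exist.** Inputs from Section 6.0 are 3 words, 3 nonword strings and 3 inks.
- Word-ink pairs: 3 × 3 = 9, of which 3 are congruent and 9 − 3 = 6 incongruent.
- Nonword-ink pairs: 3 × 3 = 9.
- Total: 9 + 9 = 18.

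On this description a new version can change trial order, timing or the proportion of trial types. It cannot introduce a new word-ink pair.

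**Step 2: where practice sits.** Count one occasion for each practice and each scanner run of either Stroop task, two tasks per visit.
- Before the baseline scan: 2.
- Before the Visit 2 scan: 2 + 2 (baseline runs) + 2 (new practice) = 6.
- Before the Visit 3 scan: 6 + 2 + 2 = 10.

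These occasions are not of equal weight, because a few examples on a computer are less than a scanner run. The count shows only that exposure rises at every scan.

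**Step 3: what an assumed practice gain does to a baseline comparison.** The plan gives no figure for practice to reproduce. Inputs are n = 16 completers and within-subject correlation ρ = 0.5 (Section 3.0, Sample Size) and one-sided α = 0.05 (Section 13.0). The practice gain p, in SD units, is an assumption shown as a range. The true rTMS effect is set to zero.

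For one post-stimulation scan minus baseline, the SD of the change is √[2(1 − ρ)] = √[2(1 − 0.5)] = 1, so the standardized change is p. For the mean of both post scans minus baseline, the variance is 1 + (1 + 0.5)/2 − 2 × 0.5 = 0.75, so the standardized change is p/√0.75. The chance of a significant result is the upper tail, beyond the one-sided critical value, of a noncentral t with 15 df and noncentrality √16 = 4 times the standardized change.

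| Assumed p (SD) | Noncentrality, one post scan (4p) | One post scan vs baseline | Mean of both post scans vs baseline |
|---|---|---|---|
| 0 | 0 | 0.05 | 0.05 |
| 0.1 | 0.4 | 0.10 | 0.11 |
| 0.2 | 0.8 | 0.19 | 0.22 |
| 0.3 | 1.2 | 0.31 | 0.37 |
| 0.4 | 1.6 | 0.45 | 0.55 |

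**Step 4: is the site contrast affected?** Let practice add p at scan 2 and 1.5p at scan 3. In the LDLPFC-first order, LDLPFC minus LSPC carries p − 1.5p = −0.5p. In the LSPC-first order it carries +0.5p. The equal-weight average is 0. A simulation of 20,000 trials (8 subjects per order, ρ = 0.5) agrees: with p = 0.2 and p = 0.3 the site contrast was significant in about 5% of runs. LDLPFC versus baseline, in the same runs, was significant in 24% and 41%.

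**The case against.** The strongest reply is that the protocol claims only mitigation, that varied trial order can limit sequence learning, and that practice before baseline may already absorb some early learning. That is fair, but nothing shows how much is absorbed, since no criterion has to be met, and no mechanism is given by which versions would limit learning of the task itself.

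A second reply is that the false-positive rates rest on assumed gains and on a paired test that Section 13.0 does not name. This stands: the figures show sensitivity and do not predict what will happen. A paired comparison is the simplest form of the baseline-to-post question.

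Third, if performance were scored as incongruent minus control trials, learning that helps all trial types equally would cancel. This is also fair, but the plan defines no score, and improved handling of conflict would not cancel.

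Three stronger readings are tempting, and the documents do not support them:
- A reader might infer that the color-to-button mapping is the same in every version. The words *randomly assigned* may refer to the mapping or to the ink shown, so the mapping is unspecified. The 18-stimulus count does not depend on it.
- A reader might infer that practice biases every comparison. Counterbalanced site order protects the LDLPFC-versus-LSPC contrast from additive practice (Step 4).
- A reader might infer that practice falsely supports the primary ACC aim. The task and scan order are the same, so practice is confounded there too, but the documents give no direction for its effect on activation.

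**Conclusion.** The point holds for change from baseline in task performance. The stated safeguard cannot prevent learning of the task, and the design has no unstimulated or sham repeat scan from which practice could be estimated and removed. With no rTMS effect, an assumed gain of 0.1 SD doubles the nominal 0.05 error to 0.10 for a single post scan, and 0.4 SD takes it to 0.45. These figures assume 16 completers, correlation 0.5, a one-sided paired test and an additive practice shift; the size of the shift is not in the documents. The consequence is limited to an exploratory aim of a pilot study. No false-positive claim is made for the site contrast or for ACC activation.

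**What to change.** In Section 6.0, replace the mitigation sentence with the following provisions:

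1. Before the baseline scan, each subject practices all trial types (nonword, congruent and incongruent) to a preset accuracy, with a maximum number of blocks for those who do not reach it. The same type of practice is used before later scans. Nonword trials alone would not be enough: the baseline scan would then be the first exposure to conflict, and early conflict learning would fall between baseline and Visit 2.
2. The color-to-button mapping is held constant within a subject at all three scans.

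In Section 13.0, add two items:

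3. Report the Visit 2 to Visit 3 performance change, averaged equally over the two site orders, as a descriptive estimate of later practice only. It may understate early learning and can include carryover from the first session, so it should not be used as a correction.
4. State that baseline-to-post performance change cannot by itself be attributed to rTMS.

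The cost is a slightly longer Visit 1, more so for slower learners, plus a short protocol edit and one extra descriptive estimate. These steps reduce and expose the confounding; they do not remove it.

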7.0 Safety Assessments

Vital Signs

A seated blood pressure and pulse will be assessed at study visits per Study Procedures Table (Attachment 1).

Medical History

The subject's lifetime medical history will be taken during the screening period. Medical history includes previous and current diseases.

Physical Examination

A physical examination including a neurological examination will be conducted as outlined in the Study Procedures Table.

8.0 Laboratory Assessments

A urine pregnancy test will be conducted in all female subjects, and a urine drug screen will be conducted in all subjects, as outlined in the Study Procedures Table.

9.0 Concomitant Medication

See Attachment 2.

10.0 Adverse Events

Adverse events (AEs), especially those for which the relationship to study treatment is not "unrelated," will be followed up until they have returned to baseline status or stabilized at the discretion of the PI. If after the follow-up period, return to baseline or stabilization cannot be established an explanation will be recorded in the source documentation.

11.0 Criteria for Repeat Assessments, Rescreening, and Discontinuation

Repeat Assessments

Screening assessments can be repeated within the screening window under the same screening number with the exception of eligibility criteria related rating scales/questionnaires. Subject diagnosis confirmation will not be repeated.

Rescreening

Subjects who screen fail may be rescreened one time, under the same screening number. If a subject is rescreened, all screening assessments (with the exception of the diagnosis confirmation) must be repeated and the stability criteria timelines must be met.

Discontinuation

Subjects will be discontinued under the following circumstances:

- 1. Subjects unwilling or unable to complete study assessments or procedures
- 2. Subjects who experience seizure occurrence at any point during study participation
- 3. Subjects who require a change in dose of antipsychotic medication or the addition of a new antipsychotic medication
- 4. Subjects experiencing an exacerbation of illness requiring an increased level of care or one judged to be clinically significant by the PI.

If subjects discontinue from the study, completion of discontinuation assessments will be at the discretion of the PI. A subject may withdrawn from the study at any time at his/her own request, or may be withdrawn at any time at the discretion of the PI for safety, behavioral, or administrative reasons.

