3.0 Study Design

This will be a single site pilot study. 20 subjects with EPP, defined as medical record documentation of the onset of clinically significant psychotic symptoms within the past 10 years, will be enrolled. Prior to randomization subjects will undergo fMRI during CC task (Stroop Color-Word paradigm) and resting-state paradigms. This baseline scan will also

include a high-resolution structural sequence for neuronavigation purposes. Then, on two separate days, each occurring one-week apart, subjects will receive one session of excitatory (20 Hz) rTMS targeting the LDLPFC and one session targeting the LSPC. The order of stimulation sites will be randomized and counter-balanced. Immediately following each session, subjects will undergo repeat fMRI during CC and RS paradigms. We will also examine the effect of rTMS on CC performance.

rTMS Set up and Administration

rTMS will be delivered using the Magventure MagPro X100 Magnetic Stimulator (Magventure Inc., Alpharetta, Georgia). Motor threshold (MT) will be determined using single pulse stimulation over the left primary motor cortex, assessed as the lowest intensity producing five visible movements of the right abductor pollicis brevis out of ten stimulations.

High Frequency rTMS

High frequency rTMS, or rTMS greater than 5 Hz, leads to faciliatory effects on brain excitability^{20-24,31}. Previous studies have demonstrated that administration of as little as a single train or a small number of trains are able to produce an immediate increase in cortical excitability²⁴. Additionally, earlier investigations have utilized high frequency rTMS in schizophrenia populations, demonstrating that the treatment is safe, well-tolerated and capable of altering cognitive performance^{30,32}. Our group has employed 20 Hz rTMS at 110% of motor threshold in a stimulation protocol in-line with the current proposal to improve cognitive function in an EPP cohort³⁰. High Frequency rTMS Protocol: Subjects will receive two sessions of HF rTMS, targeting the LDLPFC and LSPC, within the following stimulation parameters: 20 Hz, at 120% of MT, 60 trains (1.0 second per train), 20 pulses per train, inter-train interval of 20 seconds, for a total of 1200 pulses over 21 minutes. This stimulation protocol is within safety limits for rTMS^{21,33,34}.

Neuronavigation

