Brainsight software (Rogue Research, Montreal Canada) will be used to reliably target the LDLPFC and LSPC for stimulation. First, the subject's individual anatomy will be registered stereotactically using the acquired structural MPRAGE brain image and fiduciary points on the scalp visible with a Polaris vicar camera (Brainsight software). We will use the centers of mass of the LDPLFC and LSPC (derived via Freesurfer parcellation; Destrieux Atlas³⁵; left/right combined) to identify the specific coordinates for stimulation. Stimulation sites will be marked on a swim cap worn by the subjects at each stimulation session, consistent with prior TMS studies²⁵.

Electrical field modeling

The processed structural image will be used to generate E-fields based on realistic conductor head models using SimNIBS (2.1 or latest version). SimNIBS includes volume conductor

modeling (following FreeSurfer segmentation), TMS coil specific magnetic dipole estimations, and finite element modeling of the electric field at each tetrahedral element of the subject's head mesh. In anticipation of actual TMS sessions with each patient, we will find the optimal TMS positioning to most strongly influence the LDLPFC and LSPC, which will be the target for neuronavigated rTMS delivery.

rTMS administration monitoring

All subjects will be instructed to wear earplugs during each rTMS session and will be monitored by medically trained research staff throughout the entirety of each rTMS session.

Duration of Treatment

Subjects will complete two stimulation sessions over two weeks, with one session occurring each week. Previous work has demonstrated that a single session of rTMS is sufficient to modulate target site functional activation as well as functional connectivity between the stimulation target and associated circuitry²⁵.

Sample Size

We plan to enroll 20 subjects and anticipate a 20% drop out rate, yielding 16 completers. This is consistent with our previous clinical trial efforts, including a study of adjunct rTMS in an EPP cohort^{30,36}. For all planned analyses, a total of 16 subjects in a counter-balanced design will result in 0.8 power to detect an assumed stimulation effect at medium effect size 0.6; using an alpha level of 0.05 and conservatively assumed a within-subject correlation of 0.5. As no CCN rTMS pilot data was available, this standardized effect size of 0.6 is considered a conservative estimate to detect significant results.

Clinical Research Site

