13.0 Statistical Considerations

Analyses

Power Analyses

In terms of the power to detect a significant effect of HF rTMS on CC neurocircuitry or performance, there are no known calculations with EPP patients. However, previous investigations, including our own, used similar stimulation designs when investigating the effects of rTMS on overall cognitive performance. These studies demonstrated statistically significant results with sample sizes consistent with the current proposal³², and Cohen's effect sizes of d = 0.92 and 1.15, respectively^{30,32}. Though these previous studies examined different cognitive constructs than the CC task in this current protocol, these studies do provide evidence that a similar stimulation design is sufficient to elicit a biologic response and assumedly appropriate for investigating the effects of rTMS on CC.

We believe that for the purpose of this pilot study, we can demonstrate significant results with a sample size of 16 (eight per group). This accounts for the effect size estimate derived from the literature, d = 1.1, and the estimation of power to detect an effect at .75, utilizing a one-sided independent test and significance levels of 0.05.

Statistical Analyses

Preliminary analyses will consist of descriptive statistics for all outcome variables, including summary statistics, graphical displays of distributions, and spaghetti plots of individual data over time to detect possible data errors. Demographic and clinical characteristics at baseline will be examined using parametric or nonparametric test statistics as appropriate. Any demographic variables that show significant differences will be added to the final models as covariates in order to ensure that the observed stimulation effects are not spurious or due to demographic confounds.

To minimize the potential for Type II error, all treatment comparisons will be evaluated based on a one-sided significance level of 0.05. To compare overall effect of stimulation over time for the two groups, a set of multivariate repeat measures analysis of variance (ANOVA) will be utilized, with stimulation as the between-group factor and time as the within-subject factor.

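### The plan has no rule for keeping scans obtained before discontinuation, and its named ANOVA would normally drop subjects who stop between Visits 2 and 3

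*Combined protocol and SAP*

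**What the plan says.** - **Timing of the outcome.** Section 3.0: "Immediately following each session, subjects will undergo repeat fMRI during CC and RS paradigms". Section 6.0 aims to scan within fifteen minutes of a session. The Study Procedures Table (Attachment 1) puts the baseline scan at Visit 1, randomization of site order and the first post-stimulation scan at Visit 2 (Day 0), and the second at Visit 3 (Day 7). Visit 4 (Day 21) has no scan and may be a phone call.
- **Numbers.** Section 3.0, Sample Size: "We plan to enroll 20 subjects and anticipate a 20% drop out rate, yielding 16 completers". The same paragraph rests power for every analysis on that number: "a total of 16 subjects in a counter-balanced design will result in 0.8 power to detect an assumed stimulation effect at medium effect size 0.6". The inputs given there are α = 0.05, with no sidedness, and a correlation of 0.5 between a subject's measurements.
- **Analysis.** Section 13.0: "a set of multivariate repeat measures analysis of variance (ANOVA) will be utilized". Its between-group factor is stimulation and its within-subject factor is time. On testing, the section says that "all treatment comparisons will be evaluated based on a one-sided significance level of 0.05".
- **Discontinuation.** Section 11.0 lists four triggers. They include "Subjects unwilling or unable to complete study assessments or procedures", "Subjects who require a change in dose of antipsychotic medication or the addition of a new antipsychotic medication" and clinical exacerbation. On what follows, it says only that discontinuation assessments are left to the investigator.
- **Not stated anywhere.** An analysis population, a definition of completer, a missing-data rule, and whether scans taken before discontinuation are kept or excluded.

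**The concern.** Each post-stimulation scan is finished on the day of its session. A subject who completes Visit 2 and stops before Visit 3 has already given a baseline scan and a post-rTMS scan for one site, and nothing that happens later can change that pair. A repeated-measures ANOVA in its multivariate form needs all occasions, so by default it omits that subject. Nothing in the plan overrides the default, and basing power on 16 completers fits it.

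Two things are at stake. The first is precision, in a pilot of 20. The second is who the result describes. Exacerbation and antipsychotic change reflect illness state, so leaving out the subjects who meet those triggers tilts the analysis towards patients who stayed stable. In addition, losses after allocation can unbalance the two site orders. Without a clearly specified period term, part of any session effect then enters the comparison of sites.

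**Working it through.** **Inputs.** From Section 3.0: 20 enrolled, 20% dropout, effect 0.6, within-subject correlation ρ = 0.5. From Section 13.0: one-sided 0.05. Assumptions: unit variance, equal correlation among the three scans, completers 8/8 by order, retained partial subjects split evenly by site. The timing of dropout is not in the documents, so it is varied.

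**1. The plan's own figures.** 20 × (1 − 0.20) = 16, as stated. For a paired contrast the SD of the difference is √(2(1 − 0.5)) = 1, so the noncentrality at n = 16 is 0.6 × √16 = 2.4. Power from the noncentral t on 15 df is 0.74 one-sided and 0.61 two-sided. The stated 0.8 is not reached in this plain form. That is a separate matter, and 0.74 serves here as the starting value.

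**2. Pooled post-minus-baseline contrast.** Let nB, nF and nS be the numbers of baseline, first post-stimulation and second post-stimulation scans used. At ρ = 0.5, with a period term coded within the two post-stimulation scans, generalised least squares gives

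Var = 1/(4nB) + 1/(3nF) + 1/(6nS).

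The first term is (1 − ρ)²/nB, from the baseline mean. The other two come from the post-stimulation scans adjusted for baseline (residual variance 0.75, residual correlation 1/3).

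| Case | nB, nF, nS | Variance | Reduction |
|---|---|---|---|
| Completers only | 16, 16, 16 | 0.0156 + 0.0208 + 0.0104 = 0.0469 | – |
| All four stop after Visit 2 | 20, 20, 16 | 0.0125 + 0.0167 + 0.0104 = 0.0396 | 16% |
| Two after Visit 2; two earlier, baseline scans used | 20, 18, 16 | 0.0125 + 0.0185 + 0.0104 = 0.0414 | 12% |
| Two after Visit 2; two earlier, not used | 18, 18, 16 | 0.0139 + 0.0185 + 0.0104 = 0.0428 | 9% |
| All four before Visit 2, not used | 16, 16, 16 | 0.0469 | 0% |

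If all four leave before Visit 2 but their baseline scans enter the model, the variance is 0.0125 + 0.0208 + 0.0104 = 0.0437, which is 7% lower. That gain comes only from a better estimate of the baseline mean. At ρ = 0.3 and 0.7 the ceiling is 16% and 15%.

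**3. One site against baseline.** This variance is the pooled variance plus a quarter of the LDLPFC-minus-LSPC variance. Completers: 0.0469 + 0.0625/4 = 0.0625. With all four retained: 0.0396 + 0.0577/4 = 0.0540, which is 14% lower, an effective n of 1/0.0540 = 18.5. The noncentrality becomes 0.6/√0.0540 = 2.58. On about 17 df, one-sided power is about 0.80, against 0.74. For LDLPFC against LSPC it goes from 0.74 to 0.77.

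**4. Order balance among completers.** Suppose 10 subjects per order are allocated and 4 of the 20 then drop at random:
- 8/8: C(10,2)²/C(20,4) = 2025/4845 = 0.418, so the chance of imbalance is 58%.
- 9/7: 2 × 10 × 120/4845 = 0.495. The site contrast takes (9 − 7)/16 = 12.5% of any session effect.
- 10/6: 2 × 210/4845 = 0.087. The site contrast takes (10 − 6)/16 = 25%.

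The leakage cancels from the pooled contrast. Each one-site contrast moves by half the stated share, in opposite directions. Because order is randomized at Visit 2, the 58% needs all four losses to come after allocation.

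**5. Coding of the period term.** Baseline is always the first scan. If session is a three-level factor beside condition, the design matrix has rank 4 for 5 columns. If session is linear (1, 2, 3), the pooled variance is 0.158 even with all four partial subjects kept, more than three times 0.0469. The variances in steps 2 and 3 need the period coded only within the post-stimulation scans.

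**The case against.** A reader might infer that the plan discards these scans, or that it has decided to analyse 16 completers. The documents do not support that. The figure of 16 is a sample-size assumption, and Section 11.0 governs participation, not data. Exclusion follows only from the usual behaviour of the named method.

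A reader might also infer that an event between Visit 3 and Visit 4 costs data. It need not: such a subject already has all three scans, and even a complete-case ANOVA can use them.

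The reach is narrow too. Only losses in the week between Visits 2 and 3 waste a post-stimulation scan, while up to 30 days may pass before Visit 2. The 16% therefore needs all four losses in that one week. The 25% leakage belongs to a split with probability 8.7%. Section 2.0 states no hypothesis of a difference between sites, and Section 13.0 does name time as a factor, though its coding is unclear.

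All of this stands, and it limits the size of the point. It does not fill the gap: the plan names a method that needs complete data, expects dropout, and gives no rule for incomplete subjects.

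**Conclusion.** The point holds as a gap with a default consequence. There is no analysis population or missing-data rule, and the named ANOVA as usually run would drop a subject who leaves between Visits 2 and 3, together with a valid pair of scans. The gain from keeping those scans is modest and depends on timing that the plan does not give. The variance reduction for the pooled contrast runs from 0% to a ceiling of 16%, and power for one site against baseline rises by at most about 6 points, from 0.74 to 0.80. These figures assume ρ = 0.5, equal correlations and approximate degrees of freedom.

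Order imbalance is a secondary matter. It is likely if all losses follow allocation, is most often 9/7, and bears on the comparison of sites, not on the pooled effect. The possible tilt towards stable patients cannot be sized from the documents.

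**What to change.** In Section 13.0:

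- State that every usable scan obtained before discontinuation is analysed, and that one missed or unusable scan does not remove a subject's other scans. Say whether subjects with only a baseline scan are included.
- Replace the multivariate ANOVA with a linear mixed model: REML, a subject random effect, small-sample degrees of freedom, and condition as baseline, LDLPFC or LSPC.
- Add a period term coded only within the post-stimulation scans, for example 0 at baseline, −0.5 at the first and +0.5 at the second. Do not use a session number that includes baseline, because it is confounded with the baseline condition.
- Report the complete-case analysis as a sensitivity analysis, with complete defined by the scans a subject has and not by attendance at Visit 4.

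The cost is a few sentences and a routine model, with no extra subjects or visits and no change to the discontinuation rules. The downside is reliance on a missing-at-random assumption and a mixed-model fit in a very small sample. The model cannot separate a practice effect between baseline and the later scans from stimulation, because baseline always comes first.
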